# 4.0 INTRODUCTION

# 4.1 Background

Inhibition of D-amino acid oxidase (DAO) has been proposed as a potential for the treatment of schizophrenia. DAO is a peroxisomal enzyme active toward neutral D-amino acids, which is expressed in both the periphery and the brain. DAO degrades D-amino acids by oxidation. In the periphery, this action likely plays a role in the detoxification of D-amino acids from bacterial and other sources, as amino acids used for protein synthesis and other metabolic processes are L-amino acids. Few D- amino acids are known to play a biological role in humans, but D-serine in the brain has been connected to the regulation of glutamatergic neurotransmission [1], and D-serine has been shown to be an obligatory co-agonist of N-methyl-D-aspartate (NMDA)-type glutamate receptors, binding to the glycine site. Inhibition of DAO elevates endogenous D-serine in the cerebellum, increasing Purkinje cell long term depression via activation of  $\delta 2$  glutamate receptor and/or NMDA receptors with subsequent internalization of AMPA ( $\alpha$ -amino-3-hydroxy-5-methyl-4-isoxazole propionic acid)-type glutamate receptors [2].

Hypofunction of NMDA receptors is considered a possible mechanism in the pathophysiology of schizophrenia, which could be mitigated by increasing D-serine levels in the brain [3]. Changes in D-serine levels or in the ratio of D-serine to total serine have been reported in the plasma of patients with schizophrenia, both naive and under drug treatment [4-7]. In addition, serine racemase (the D-serine generating enzyme) and the NMDA NR2A subunit are among the risk genes identified from the recent large scale genome-wide association study analysis, indicating the biological relevance to schizophrenia of the genetic pathway in which DAO sits [8].

Adding to the above evidence of a potential role of DAO in the pathophysiology of schizophrenia, a weak inhibitor of DAO, sodium benzoate, demonstrated efficacy in positive, negative, and cognitive symptoms in a proof-of-concept study in subjects with schizophrenia [9].

While current medications mitigate positive symptoms of schizophrenia and to some extent the negative symptoms, cognitive impairment represents an area of unmet medical need. Moreover, cognitive and negative symptoms are associated with functional outcomes to a greater degree than positive symptoms and remain an area of focus for the development of novel therapeutics.

# 4.2 Rationale for the Proposed Study

TAK-831 is a highly selective and potent inhibitor of DAO. TAK-831 was shown to increase D-serine levels in the cerebellum of normal rats, and it also demonstrated a positive effect on cognition and social interaction in rodent cognition and behavioral models. TAK-831 is under development for the treatment of negative symptoms of schizophrenia (NSS) and cognitive impairment associated with schizophrenia (CIAS), as well as for cerebellar ataxias such as Friedreich ataxia. In addition to safety and tolerability, the current proposed study is aimed at providing information on the relationship between concentrations of TAK-831

#### 4.3 Benefit/Risk Profile

There is no benefit to subjects in this clinical study.

The following risk mitigation measures will be implemented in this study with TAK-831. These measures are based on what is known about the mechanism of action of TAK-831, nonclinical data, and the 2 phase 1 studies conducted to date. Procedures may be added during the study if necessary based on evaluation of any additional clinical or nonclinical safety data.

- TAK-831 has been used in a prior single dose (up to 750 mg in oral suspension and 100 mg in tablet T1 formulation and 14 days multiple dose (up to 400 mg QD in oral suspension) study in healthy subjects (TAK-831-1001) with good safety and tolerability, as well as a single dose PET study (TAK-831-1003), and these studies have not resulted in a safety signal that would prevent additional studies. Additionally, a T2 tablet formulation is currently under assessment in a single dose food effect study (TAK-831-1004) that will contribute additional data to inform dose selection during the conduct of this study.
- Acute hypersensitivity/anaphylactic reactions to new chemical entities are always a possible risk in any clinical study. Appropriate procedures should be used to manage such possible risks.
- Study procedure—specific risks include issues relating to blood collection for safety assessment/PK and PD monitoring (venipuncture may cause bruising), and the placement of ECG pads, which may cause some local redness and/or erythema/itching.
- The risk of pain or discomfort at the site of CSF collection and the risk of headache in cohorts where CSF will be collected for PK and PD assessment. Severe headaches may require a blood patch procedure. There is a small risk of infection with indwelling catheters.
- The investigator has discretion to use his/her clinical judgment as to whether to allow a subject to proceed in the study or whether to unblind the subject in order to determine his/her treatment allocation.
- The C-SSRS will be administered to monitor emergent suicidality.

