# 6.1 Trial Design

The study is an investigator and subject blinded, sponsor unblinded, placebo-controlled clinical study progressively assessing independent cohorts of healthy subjects to continue evaluation of the safety, tolerability, and PK of escalating single doses (SD) and multiple doses (MD) of TAK-831, as either a suspension or T2 tablet formulation, at levels higher than those achieved in the initial single and multiple rising dose (SRD/MRD) Study TAK-831-1001.

Up to 6 cohorts will be run either singly or in parallel as non- cerebrospinal fluid (CSF) cohorts with plasma analysis or CSF cohorts with CSF analysis in addition to plasma analysis to assess TAK-831 exposure and levels in the central nervous system (CNS). After meeting all the selection criteria, there will be 8 subjects enrolled in each cohort. They will be randomized on Day 1 in a 1:3 ratio to receive placebo or TAK-831.

All cohorts will start with an initial, in-house SD period to include predose PD assessments on Day -1, Day 1 TAK-831 dosing, and a 48-hour in-house observation period with full PK collections. The SD PK collection and observation phase will be followed by 14 days of in-house MD.

In CSF cohorts, lumbar CSF samples will be collected through either a single lumbar puncture or an indwelling temporary catheter on 2 separate occasions. In CSF cohorts that use an indwelling temporary catheter on both occasions, the first collection will occur on Day 1, and the second on Day 16. In CSF cohorts where the pre-dose CSF sample is collected through a single lumbar puncture, the first CSF sample will be collected on Day -1 prior to the start of monitoring and the second collection will be obtained through use of an indwelling temporary catheter on Day 16. If an indwelling temporary catheter is being used, it will collect serial CSF samples for 24 hours.

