Since, the highest dose tested in single rising dose portion of Study TAK-831-1001 was 750 mg administered as a suspension, all dose levels above 750 mg/day will be tested first in SD setting before MD in subsequent cohorts.

All decisions concerning dose escalation will be made by Takeda (at a minimum, the clinical science representative[s], quantitative clinical pharmacologist, study statistician and pharmacovigilance physician) and the principal investigator. The investigator and subjects will remain blinded throughout the study, but at the completion of each cohort, specific Takeda personnel listed in associated study documentation may be unblinded to analyze data considered necessary to determine subsequent doses and cohort management decisions. All data presentations prepared for discussions with the investigator and site staff will contain only blinded study data, except in the event that formal study unblinding procedures detailed in Protocol Section 8.1.5 have been followed and discussion of related data is required.

If agreement regarding a dose escalation decision cannot be reached between the principal investigator and Takeda, the study will be stopped.

Based on emerging safety and tolerability and PK data, the planned dose levels may be modified.

All adverse events reported during the Treatment Period, both within and across cohorts, up to the time of discharge will be evaluated to assess the need for subject and/or study termination in accordance with the prespecified criteria for discontinuation/termination (Section 6.5).

Following assessment of the adverse event data and predefined criteria for study termination, dose escalation may be interrupted/stopped if these criteria are met. Based on review of study data as outlined above, Takeda, in consultation with the principal investigator, will decide if and how it is appropriate for the study to proceed.

Dose escalation may be interrupted/stopped if:

- Exposures in any cohort exceed those observed at the top dose tested in the monkey toxicity study, that is, a mean  $C_{max}$  of 3680 ng/mL or a mean  $AUC_{24}$  of 35,700 hr\*ng/mL.
- The exposures reach the plasma exposure plateau in the 2 highest dose cohorts.
- One or more subjects in any single cohort or across more than 1 cohort experience an SAE or 2 severe or clinically significant AEs occur that are considered related to study drug.

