#### 8.1.5 Clinical Trial Blind Maintenance/Unblinding Procedure

The investigational drug blind is maintained through a randomization schedule held by the randomization personnel.

The investigational drug blind shall not be broken by the investigator unless information concerning the investigational drug is necessary for the medical treatment of the subject. The investigator should perform all study assessments and causality evaluation, if possible, before unblinding. In the event of a medical emergency, if possible, the medical monitor or designee should be contacted before the investigational drug blind is broken to discuss the need for unblinding. The sponsor must be notified as soon as possible if the investigational drug blind is broken.

Individual code break envelopes will be provided for all subjects to the investigator or designee by the sponsor or designee. Each sealed envelope containing the randomization code and treatment will be kept in a medication storage room, which is locked with restricted access. If opened, the name of the person who opened it, the date and time of opening and the reason for opening must be written on the envelope. A similar mechanism may be substituted for envelopes (eg, scratch-off cards).

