# 9.1.1.1 Assignment of Screening and Randomization Numbers

All consented subjects will be given a unique screening number that will be used to identify the subject for all procedures that occur before randomization or allocation. Each subject will be assigned only 1 screening number. Screening numbers must not be re-used for different subjects. Any subject who is screened multiple times will be assigned a new screening number for each screening event.

Subjects who qualify for the study will be assigned a 4-digit randomization sequence number starting with X001 in the order in which they are enrolled into their respective Cohort X, and ended with X008. For example, for Cohort 2, the randomization numbers will be 2001 to 2008. The number will be assigned by the clinic site personnel in sequential order beginning and ending with the numbers specified for each cohort. The 4-digit randomization number will dictate which treatment will be assigned to each subject based on the randomization schedules distributed only to the authorized personnel (eg, pharmacist). Once a randomization number is assigned to a subject, it can never be reassigned to another subject. A single subject cannot be assigned more than 1 randomization number.

For a subject's replacement, the randomization number will be X9XX, where X's are the same as those for the original subject. For example, the replacement number for Subject 3005 will be 3905. The replacement will be given the same drug as that for the original subject.

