## **Pregnancy**

Women of childbearing potential will not be included in this study.

If any subject is found to be pregnant during the study she should be withdrawn and any sponsor-supplied drug should be immediately discontinued. In addition, any pregnancies in the partner of a male subject during the study or for (5 half-lives PLUS 90 days) after the last dose, should also be recorded following authorization from the subject's partner.

Should the pregnancy occur during or after administration of blinded drug, the investigator must inform the subject of their right to receive treatment information. If the subject chooses to receive unblinded treatment information, the individual blind should be broken by the investigator. Subjects randomized to placebo need not be followed.

If the female partner of a male subject agrees to the primary care physician being informed, the investigator should notify the primary care physician that the female partner of the subject was participating in a clinical study at the time she became pregnant and provide details of the study drug the subject received (blinded or unblinded, as applicable).

All pregnancies, including female partners of male subjects, in subjects on active study drug (including comparator, if applicable) will be followed up to final outcome, using the pregnancy form. Pregnancies will remain blinded to the study team. The outcome, including any premature termination, must be reported to the sponsor. An evaluation after the birth of the child will also be conducted.

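### Protocol Section 4.3 lets the investigator unblind by judgment to learn the allocation, while Section 8.1.5 forbids it unless medical treatment requires it; the two, and the Appendix D pregnancy route, need reconciling

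*Protocol*

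**What the plan says.** Four places in the protocol bear on when the investigator may learn a subject's treatment.

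- **Section 4.3 (Benefit/Risk Profile)** lists measures to be implemented in the study. One bullet gives the investigator discretion, by clinical judgment, over two things: whether a subject proceeds, and "whether to unblind the subject in order to determine his/her treatment allocation".
- **Section 8.1.5 (Clinical Trial Blind Maintenance/Unblinding Procedure)** is a prohibition with one exception. The blind "shall not be broken by the investigator unless information concerning the investigational drug is necessary for the medical treatment of the subject". It also says that "Individual code break envelopes will be provided for all subjects to the investigator or designee", so a break concerns one subject at a time.
- **Section 6.2 (Dose Escalation)** expects the investigator to stay blinded throughout. It restricts data shown to the site to blinded data, "except in the event that formal study unblinding procedures detailed in Protocol Section 8.1.5 have been followed".
- **Appendix D (Pregnancy)** says that, if the subject chooses to receive treatment information, "the individual blind should be broken by the investigator". Appendix B has the related consent wording.

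Two design features determine how far a break reaches. Section 6.1 says of each cohort's subjects: "They will be randomized on Day 1 in a 1:3 ratio to receive placebo or TAK-831". Section 11.3 gives the split as 6 active and 2 placebo in each cohort of 8. Section 9.1.1.1 says: "The replacement will be given the same drug as that for the original subject". The replacement carries a number linked to the original's (3905 for 3005).

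**The concern.** Sections 4.3 and 8.1.5 give different answers to one question: may the investigator open a code to find out what a subject received, when treatment of that subject does not depend on it? Under 4.3, clinical judgment is enough. Under 8.1.5, it is not.

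The sponsor side of this trial is open, so the investigator's blind is the main protection for assessments that involve judgment. The causality call is one of these. It enters the Section 6.2 criteria on related severe or clinically significant events and on related psychiatric symptoms, and it defines the drug-related TEAE tables in SAP Section 8.11.1. The principal investigator also takes part in escalation decisions, and disagreement with the sponsor stops the study. Once a code is open, later causality calls in that subject are no longer blinded. The same holds for a replacement known to be on the same drug.

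**Working it through.** **Step 1. Compare the rules.**

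| Place | Who decides | Condition | Refers to 8.1.5? |
|---|---|---|---|
| 4.3 | Investigator | Clinical judgment; the stated purpose is to learn the allocation | No |
| 8.1.5 | Investigator; medical monitor contacted first in an emergency if possible | Necessary for the subject's medical treatment | – |
| Appendix D | Subject's choice after a pregnancy | None tied to medical treatment | No |

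Suppose an investigator opens an envelope to help decide whether a subject should continue, and no treatment decision depends on the answer. This fits 4.3 and breaches 8.1.5. A pregnancy break fits Appendix D but is not among the exceptions in 8.1.5.

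**Step 2. Reproduce the cohort split.** Inputs: 8 subjects and a 1:3 placebo-to-active ratio (Section 6.1).

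- Active: 8 × 3/4 = 6. Placebo: 8 × 1/4 = 2. This agrees with Section 11.3.
- Possible placebo pairs: C(8,2) = 8 × 7 / 2 = 28, all equally likely before any break.
- Chance that a given subject is on active drug: 6/8 = 75.0%.

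**Step 3. What one break says about the other seven original subjects.**

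- Placebo found (probability 2/8 = 1/4). The other seven hold 6 active and 1 placebo, so the chance of active is 6/7 = 85.7%, a rise of 10.7 points. Assignments still possible: 7.
- Active found (probability 6/8 = 3/4). The other seven hold 5 active and 2 placebo, so the chance of active is 5/7 = 71.4%, a fall of 3.6 points. Assignments still possible: C(7,2) = 21.
- Check: 1/4 × 6/7 + 3/4 × 5/7 = 6/28 + 15/28 = 21/28 = 75.0%.

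In neither case is any other original subject's treatment determined.

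**Step 4. When the rest become certain.** This needs both placebo codes or all six active codes to be open. For randomly chosen breaks:

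- Two breaks: C(2,2)/28 = 1/28 = 3.6%.
- Three breaks: C(3,2)/28 = 3/28 = 10.7%.
- Four breaks: C(4,2)/28 = 6/28 = 21.4%.

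**Step 5. Replacements.** Under the same-drug rule in 9.1.1.1, opening the code of either member of an original–replacement pair reveals the other with certainty. This applies only where a replacement exists. Section 7.7 makes replacement case by case, at the sponsor's discretion.

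**The case against.** The strongest reply is that the passages can be read together. Section 4.3 is a general risk bullet about clinical judgment, 8.1.5 supplies the condition and the procedure, and 6.2 points to 8.1.5. On that reading, the investigator judges under 8.1.5 whether the information is needed. The reading is reasonable, but 4.3 does not say so. It names learning the allocation as the purpose and gives no cross-reference, so the wording still needs repair.

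A second reply is that safeguards exist. Section 8.1.5 asks that assessments and causality be completed before unblinding if possible, that the sponsor be told of any break, and that the name, date, time and reason be written on the envelope. Section 8.1 requires contact with the sponsor before a replacement is dosed. These count. The first protects the triggering event, but not later events in the same subject or events in a replacement.

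Third, the harm has limits. None of the four primary endpoints uses causality, escalation is a joint decision, and the Section 6.2 criteria say that escalation may be stopped, not that it must be. All of this is correct.

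A reader might infer from the fixed 6:2 split that every code break reveals other subjects' treatment. The documents do not support that: one break settles no other original subject, and the likelier result, an active code, shifts the others by only 3.6 points. Partial information of this kind arises in any small cohort with a fixed ratio. A reader might also infer that the same-drug rule must be replaced by a separate concealed list. That is a debatable trade-off. It needs a new schedule and could leave a cohort at 5:3 or 7:1, for a situation that requires a break, a discontinuation and a sponsor decision to replace.

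**Conclusion.** The protocol contradicts itself on when the investigator may unblind: 4.3 allows it by judgment, 8.1.5 only for medical treatment, and Appendix D at the subject's choice after a pregnancy. The passages must be reconciled.

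The direct loss is the blind for the opened subject's later causality calls, and for those of a linked replacement if there is one. The effect on the other original subjects is partial: 75.0% to 85.7% or 71.4% per break, with none determined by a single break.

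These figures assume that the 6:2 split is exact in each cohort, that the investigator knows it from the protocol, and that nothing else is known about the other subjects. The probabilities of finding placebo or active, and those for several breaks, also assume that the opened codes are a random choice. Breaks prompted by adverse events need not be. The documents give no expected number of code breaks or replacements, so the overall frequency cannot be estimated.

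**What to change.** Make one unblinding rule apply:

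1. In Section 4.3, change only the unblinding clause of the bullet, so that it says any unblinding follows Section 8.1.5. Section 6.2 already treats that section as the formal procedure. Leave the clause on whether a subject may proceed as it is, because 8.1.5 does not cover that discretion and replacing the whole bullet would delete it.
2. In Section 8.1.5, add a cross-reference to the pregnancy route in Appendix D, so that every permitted route can be found from one place.

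The cost is two short wording changes, with no effect on the randomization schedule, the supplies or the 6:2 split. A separate concealed list for replacements after a site code break is an option for the sponsor to weigh and is not needed to resolve the contradiction.

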#### 5.0 TRIAL OBJECTIVES AND ENDPOINTS

# 5.1 Trial Objectives

# 5.1.1 Trial Primary Objective

To evaluate the safety and tolerability of TAK-831 when administered as multiple oral doses at escalating dose levels in healthy subjects.

# 5.1.2 Trial Secondary Objective

To evaluate the PK of TAK-831 when administered as multiple oral doses at escalating dose levels in healthy subjects.

# **5.1.3** Trial Exploratory Objectives

# 5.2 Endpoints

#### **5.2.1** Primary Endpoints

Primary endpoints are the safety parameters of TAK-831 and will be assessed as follows:

- 1. Percentage of subjects who experience at least 1 treatment-emergent adverse event (TEAE)
- 2. Percentage of subjects who meet the markedly abnormal criteria for safety laboratory tests at least once postdose.
- 3. Percentage of subjects who meet the markedly abnormal criteria for vital sign measurements at least once postdose.
- 4. Percentage of subjects who meet the markedly abnormal criteria for safety ECG parameters at least once postdose.

[figure not shown]
# **5.2.2** Secondary Endpoints

Secondary endpoints are the plasma PK parameters of TAK-831 and will be measured as follows:

- 1. Maximum observed plasma concentration  $(C_{max})$  (Day 1).
- 2. Maximum observed steady-state plasma concentration during a dosing interval (Day 16).

- 3. Time of first occurrence of  $C_{max}$  (Days 1 and 16).
- 4. Area under the plasma concentration-time curve during a dosing interval (Days 1 and 16).

